1. OBJECTIVES

1.1 Study Design

This study includes a brief Phase I dose escalation to assess the tolerability of pyrimethamine in relapsed Chronic Lymphocytic Leukemia/Small Lymphocytic Lymphoma, CLL/SLL, and T-Large Granular Lymphocytic Leukemia, T-LGL, and to correlate dose with pharmacodynamic efficacy. It then moves rapidly to a Phase II study to assess efficacy, using a Simon two stage design. Due to PK and PD results that suggest that a higher dose between 100 and 150 mg may be required for optimal efficacy, and the absence of clear drug-related toxicity thus far, the protocol is being amended to continue the phase 1 dose escalation to a higher dose.

1.2 Primary Objectives

Phase I: To determine the MTD and recommended Phase 2 dose of pyrimethamine in relapsed CLL/SLL and T-LGL

Phase II: To determine the ORR of pyrimethamine in relapsed CLL/SLL and T-LGL

1.3 Secondary Objectives

- To assess the toxicity profile of pyrimethamine in relapsed CLL/SLL and T-LGL, both acutely and over prolonged daily dosing.
- To determine pyrimethamine levels in vivo with prolonged dosing.
- To determine the progression-free survival following pyrimethamine for the treatment of relapsed CLL/SLL and T-LGL.
- To determine whether pyrimethamine inhibits STAT3 in vivo by assessing downregulation of STAT3 dependent gene expression in CLL cells, and T-LGL and/or peripheral blood mononuclear cells.
- To determine whether known prognostic factors in CLL/SLL and T-LGL correlate with response to pyrimethamine.
- To assess the impact of CT scans on response evaluation in relapsed CLL/SLL and T-LGL.

2. BACKGROUND

2.1 Investigational Agent: Pyrimethamine

CONFIDENTIAL

This document is confidential. Do not disclose or use except as authorized.

Pyrimethamine (5-(4-chlorophenyl)-6-ethyl-2,4-pyrimidinediamine, Daraprim) is an oral folic acid antagonist used as an antiparasitic compound. It is a reversible weak inhibitor of dihydrofolate reductase. Due to a differential requirement between host and parasite for nucleic acid precursors involved in growth, pyrimethamine is highly selective against plasmodia and *Toxoplasma gondii*.

Pyrimethamine is well absorbed with a plasma half-life of approximately 96 hours. Pyrimethamine is 87% bound to human plasma proteins. At the maximum dose tested in this trial, namely 50 mg/day, mean plasma pyrimethamine concentrations were 1,893+/-1,182 ng/ml¹. As a folate antagonist, caution is recommended in patients with possible folate deficiency, such as individuals with malabsorption syndrome, alcoholism, or pregnancy, and those receiving therapy such as phenytoin or lorazepam, which may increase the risk of hepatotoxicity.

The 50 mg/day dose maximum proposed for this trial is the recommended dose for the treatment of toxoplasmosis, and is routinely used for at least 1-3 weeks depending on treatment response. At this dose, anorexia and vomiting may occur. Vomiting may be minimized by giving the medication with meals; it usually disappears promptly upon reduction of dosage. Doses used in toxoplasmosis may produce bone marrow suppression, which can be reversed with discontinuing the drug and with addition of leucovorin. Side effects include megaloblastic anemia, leukopenia, thrombocytopenia, pancytopenia, atrophic glossitis, hematuria, and disorders of cardiac rhythm. Hypersensitivity reactions, occasionally severe (such as Stevens-Johnson syndrome), have been reported but primarily when pyrimethamine is administered concomitantly with a sulfonamide.

Due to the possibility of myelosuppression and given the patient population in this study, we include a brief Phase I dose escalation to assess the tolerability of pyrimethamine in relapsed CLL/SLL, and to correlate dose with pharmacodynamic efficacy. The Phase I starting dose of 12.5 mg. is the lowest convenient dose available and significantly lower than the usual dose used for infectious diseases. We then move rapidly to a Phase II study to assess efficacy, using a Simon two stage design.

2.2 Study Diseases: Chronic Lymphocytic Leukemia and T Large Granular

Lymphocytic Leukemia

Chronic lymphocytic leukemia (CLL / SLL) is the most common form of leukemia in the United States with more than 13,000 new cases per year². The disease incidence increases with age and is more common in men than women. Although classified as a leukemia, the clinical behavior and treatment of CLL is more similar to many low-grade lymphomas. Patients are observed until they are deemed to require therapy based on worsening symptoms or cytopenias, increasing lymphocytosis, lymphadenopathy or splenomegaly, or transformation of disease³. Therapy has been palliative, with no established therapy shown to improve survival.

The last ten years have resulted in significant therapeutic advances, with the advent of chemoimmunotherapy combinations with complete remission rates approaching 50% and progression-free survivals of 3-5 years⁴⁻⁶. However 10-20% of patients still fail to respond or relapse early, and all patients still relapse eventually. For these patients, especially those who are

fludarabine refractory with bulky adenopathy, or those with poor risk cytogenetics, there remains an urgent need for new more effective therapies that are less toxic. The field has therefore turned to targeted drugs, designed to directly address the mechanism of carcinogenesis, in an effort to improve efficacy and reduce toxicity.

T-LGL is an uncommon low-grade lymphoproliferative disorder that can occur as an isolated entity or in the context of rheumatologic or neoplastic disease. Many patients remain asymptomatic and do not require treatment. However, some patients develop anemia (either autoimmune or hypoproliferative), neutropenia, infection, or disease related symptoms such as fatigue. Oral methotrexate and oral cyclophosphamide have been the most commonly utilized agents with response rates ranging from 38-64%⁷. These agents are not curative and can have significant toxicity including myelosuppression, mucositis, and liver function abnormalities. Other agents that have been investigated with varying success include cyclosporine and alemtuzumab^{8,9} However, cyclosporine can cause renal insufficiency and is immunosuppressive while alemtuzumab is profoundly myelosuppressive and immunosuppressive and can be challenging to obtain commercially due to marketing restrictions.

A large body of literature has emerged demonstrating the importance of STAT3 and STAT5b mutations in T-LGL. Most of these mutations are activating somatic mutations in the SH2 domain of STAT3 though other STAT3 mutations have been described^{10,11}. Therefore we propose amending the existing protocol to include patients with T-LGL. We are not requiring a demonstrable STAT3 mutation since the presence of these mutations is not clearly known to be predictive of response to STAT3 inhibitors.

2.3 Rationale

2.3.1 Biology of the STAT family of Transcription Factors

The function of lymphoid cells is regulated by cytokines which control processes such as survival, self-renewal, proliferation, and differentiation. Although cytokines activate a number of signaling pathways, increasing evidence suggests that STATs, for signal transducers and activators of transcription, play a key role in this process. STATs are present in the cytoplasm of cells under basal conditions. When stimulated by a growth factor or cytokine, STATs become phosphorylated on a unique tyrosine residue which triggers their dimerization. STAT dimers then translocate to the nucleus where they bind to specific nine base pair sequences in the regulatory region of target genes, thereby activating transcription (Figure 1). Given that STATs control genes that regulate critical biological functions including cell proliferation and survival, physiological STAT activation is rapid and transient. Roughly one hour after STAT activation, the STATs have been dephosphorylated and have returned to the cytoplasm. Although classically STATs are activated by tyrosine phosphorylation, certain STAT family members, including STAT3, have a highly conserved serine residue towards the carboxyl terminus that is also phosphorylated in a highly regulated manner. Increasing evidence indicates that phosphorylation of this residue, serine 727, can have activating effects independent of tyrosine phosphorylation^{12,13}.

[figure not shown]

Figure 1. Activation of STATs in response to cytokines or other signals leads to the regulation of genes which play a key role in cellular proliferation and survival.

Given the importance of STATs in mediating the physiological regulation of these genes, it is not surprising that inappropriate activation of STATs occurs commonly in hematologic cancers. In fact some abnormality in STAT signaling has been reported in every form of leukemia and lymphoma. We had found that STAT3 is phosphorylated on serine 727 in CLL cells isolated from essentially all patients with this disease¹⁴. Serine phosphorylated STAT3 can be found in the nucleus, and can drive expression of genes regulating survival and proliferation¹⁵. Furthermore, natural products with therapeutic activity toward CLL can decrease the serine

phosphorylation of STAT3¹⁶. Genes whose expression are activated by STAT3 control critical cellular functions such as cell survival (e.g., Mcl-1 and Bcl-xl), which is a major factor in both the pathogenesis of CLL, and its resistance to curative cytotoxic therapy¹⁷. While continued STAT3 function is critical for tumor cell survival, STAT3 can be inhibited in normal cells with little consequence¹⁸. Taken together, these findings suggest that STAT3 is an excellent target for the treatment of CLL and T-LGL.

2.3.2 Identification of STAT3 inhibitors. Given that inappropriate phosphorylation of STAT3 is observed nearly universally in CLL and appears to contribute directly to the pathobiology of CLL cells, there would be great utility in the development of small molecules that could specifically and effectively inhibit this pathway. Since the goal was to identify drugs that can be translated rapidly into human clinical trials, the Prestwick Collection, a library containing 1120 compounds most of which have already been tested in humans and are either FDA-approved or known to be safe, was screened with a STAT3 inhibition assay in the laboratory of [name], Director of the [name] Laboratory, a division of the Louis B. Mayer Research Laboratories at DFCI. See Section 8, Correlative/Special Studies.

The compound that led to the greatest specific inhibition of STAT3 activity in the initial screen was pyrimethamine, a compound that is FDA approved for treating parasitic infections such as toxoplasmosis and malaria. It is orally bioavailable and has relatively few significant side effects. Given its slow elimination, it is generally dosed once daily. Pyrimethamine shows half-maximal activity (EC₅₀) at approximately 1.5 μM, well within the plasma concentrations found with clinical use. Pyrimethamine has no effect on STAT3 phosphorylation or nuclear translocation, but it appears to inhibit STAT3 localization to its cognate genomic DNA sequences, thereby inhibiting its function. Although pyrimethamine is known as an inhibitor of dihydrofolate reductase (DHFR), albeit a weak one, the potent DHFR inhibitor methotrexate did not inhibit STAT3 activity in this assay. Therefore, STAT3 inhibition by pyrimethamine is probably distinct from its effect on DHFR. The effect of pyrimethamine was examined in MDA-MB-231 cells, which are characterized by constitutive STAT3 activation. Using quantitative RT-

PCR normalized to GAPDH, we found that 1 μ M pyrimethamine, a concentration achievable in vivo, decreased expression of Bcl-x1 and cyclin D1 by approximately 60%. Pyrimethamine showed no toxicity in non-transformed hematopoietic cells, epithelial cells, or fibroblasts.

2.3.3 Pyrimethamine shows therapeutic effects in CLL cells in vitro. In model systems, pyrimethamine effectively inhibits STAT3-dependent gene transcription at low micromolar concentrations that can be achieved clinically in humans (Figure 2). By contrast, pyrimethamine has no effect on gene expression driven by NF- κ B or the closely related transcription factor STAT5. Pyrimethamine (5 μ M) significantly decreased expression of a panel of STAT3-dependent target genes, including BCL3, BCL6, cyclin D1, and SMAD7, while showing no effect on expression of “housekeeping” genes including tubulin and GAPDH, or NF- κ B-dependent genes including A20 and TLR4. [name] lab next assessed the effect of pyrimethamine on the viability of primary CLL cells in culture. As early as 48 hours after treatment, pyrimethamine caused a significant dose-dependent decrease in survival of CLL cells, beginning at concentrations as low as 1 μ M, and it does so through induction of apoptosis as measured by annexin V staining. Thus, pyrimethamine, a well tolerated FDA approved drug, inhibits STAT3 and induces apoptosis of primary CLL cells in vitro.

[figure not shown]

Figure 2. The anti-parasitic compound pyrimethamine was the most active and specific STAT3 inhibitor among 1120 compounds screened in the Prestwick Collection.

2.3.4 Study Rationale

Based on these data, we propose a clinical trial of the STAT3 inhibitor pyrimethamine in relapsed CLL/SLL and T-LGL. The drug is FDA approved and has been well-tolerated in a wide variety of patients, suggesting that its toxicity profile is favorable. The in vitro data suggest that pyrimethamine may be highly effective against CLL/SLL in vivo, warranting a clinical test.

2.4 Correlative Studies Background

To optimally utilize pyrimethamine as a therapy for CLL, it will be essential to determine if pyrimethamine is, in fact, inhibiting STAT3 function in CLL cells. If pyrimethamine is clinically effective, then it will be important to determine the lowest dose necessary to achieve STAT3 inhibition, to minimize the chance for non-specific toxicities. If pyrimethamine does not show activity in these patients, then it will be essential to know whether STAT3 was successfully inhibited.

In order to address these questions, at the time of each clinic visit, heparinized blood samples will be drawn for several assays. First, pharmacokinetics will be performed on plasma to assess steady-state levels of pyrimethamine over time, and drug accumulation over time. Second, two pharmacodynamic assays will be performed. The first will employ quantitative flow cytometry to assess total STAT3 levels as well as phosphorylation of STAT3 in vivo in CLL cells over time. The second will use PCR to assess the expression of a panel of ten STAT3 target genes that [name] lab has found to be most informative of pyrimethamine-induced STAT3 inhibition in CLL cells treated in vitro, as well as four genes they have found to be invariant which will be used for normalization. Taken together these assays should enable us to determine whether adequate pyrimethamine levels were present and whether pyrimethamine successfully inhibited STAT3 phosphorylation and activation of target genes.

Preliminary results of PK and PD analyses from the first three dose cohorts, up to 50 mg daily, suggest that the achieved blood levels of pyrimethamine thus far may be lower than required for most effective STAT3 inhibition. For that reason we are adding dose cohorts to the Phase 1 study.

3. PARTICIPANT SELECTION

3.1 Eligibility Criteria

Participants must meet the following criteria on screening examination to be eligible to participate in the study:

Subjects with CLL/SLL:

3.1.1 Subjects must be diagnosed with CLL / SLL (chronic lymphocytic leukemia / small lymphocytic lymphoma) based on the standard histologic and immunophenotypic criteria described in the WHO classification of lymphoid malignancies, including immunophenotypic confirmation that the tumor cells co-express B cell antigens CD19 / 20 and CD5. Mantle cell lymphoma should be excluded based on positive staining of the tumor cells for CD23, or the absence of staining of the tumor cells for cyclin D1 or the absence of t(11;14). This diagnosis should be confirmed at a Dana-Farber Harvard Cancer Center institution (DFCI, BWH, MGH, BIDMC) within approximately one month after the subject is registered. Any question on histology confirmation should be brought to the attention of the Principal Investigator.

3.1.2 Participants must have measurable disease, defined as lymphocytosis \geq 5,000 / ul, or at least one palpable or CT measurable lesion $>$ approximately 1.5 cm, or bone marrow involvement $>$ approximately 30%.

3.1.3 Subjects must have relapsed after at least one prior purine analogue-containing regimen (fludarabine, cladribine or pentostatin), OR at least two non-purine analogue containing regimens.

Subjects with T-LGL:

T-LGL judged by the investigator to require therapy based upon:

- 1) Severe neutropenia (absolute neutrophil count $<$ 500/microL)
- 2) Moderate neutropenia (absolute neutrophil count $<$ 1000/microL) with recurrent infections
- 3) Symptomatic or transfusion dependent anemia
- 4) Severe thrombocytopenia ($<$ 50,000/microL)
- 5) Hepatic infiltration resulting in abnormal liver function tests
- 6) Symptomatic splenomegaly

Patients with previously untreated or relapsed/refractory disease will be eligible

All Subjects:

3.1.4 Age \geq 18 years.

3.1.5 Life expectancy of greater than 3 months.

3.1.6 ECOG performance status \leq 2 (Karnofsky \geq 60%, see Appendix B).

3.1.7 Participants must have normal organ function as defined below:

- total bilirubin $\leq 1.5X$ institutional ULN unless due to indirect hyperbilirubinemia related to Gilbert's syndrome or hemolysis, or to disease infiltration
- AST (SGOT)/ALT (SGPT) $\leq 5 X$ institutional upper limit of normal
- creatinine $\leq 2X$ institutional ULN

3.1.8 Subjects must require treatment based on IWCLL 2008 criteria (Appendix A).

3.1.9 The effects of pyrimethamine on the developing human fetus are unknown. For this reason and because pyrimethamine is teratogenic in animals, women of child-bearing potential and men must agree to use adequate contraception (hormonal or barrier method of birth control; abstinence) prior to study entry and for the duration of study participation. Should a woman become pregnant or suspect she is pregnant while participating in this study, she should inform her treating physician immediately.

3.1.10 Ability to understand and the willingness to sign a written informed consent document.

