5.5 Duration of Therapy

Initial response assessment will occur after 28 days of study therapy. Those subjects with stable or responding disease may continue on study indefinitely if their treating physician and the Principal Investigator feel that they are deriving clinical benefit. Subjects with significant adverse events or progressive disease should be removed from study.

Duration of therapy will depend on individual response, evidence of disease progression and tolerance. In the absence of significant adverse events, treatment may continue indefinitely or until one of the following criteria applies:

- Disease progression,
- Intercurrent illness that prevents further administration of treatment,
- Unacceptable adverse event(s),
- Participant decides to withdraw from the study, or

- General or specific changes in the participant's condition or compliance render the participant unacceptable for further treatment in the opinion of the treating investigator.

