5.6 Duration of Follow Up

Participants will be followed until initiation of their next therapy or until death, whichever occurs first. Their general medical condition and survival status will be followed for the duration of their life, even after additional therapies. Subjects not presenting in clinic on a regular basis may be called by the study staff when possible. Participants removed from study for unacceptable adverse events will be followed until resolution or stabilization of the adverse event.

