5.7 Criteria for Removal from Study

Participants will be removed from study when any of the criteria listed in Section 5.5 apply. The reason for study removal and the date the participant was removed must be documented in the study-specific case report form (CRF). Alternative care options will be discussed with the participant.

In the event of unusual or life-threatening complications, participating investigators must immediately notify the Principal Investigator (or Protocol Chair), [name] at [contact].

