6.3.2 Rash

For grade 3 or greater skin rash, study drug should be discontinued. If the rash resolves (back to grade 1 or less, within 4 weeks) with supportive care and is not IgE mediated or accompanied by other signs of allergic hypersensitivity, patients may resume study therapy at one lower dose level, or if already at the lowest dose level, may resume at that dose with addition of prophylactic antihistamine. Consideration may be given to use of a prophylactic antihistamine, particularly diphenhydramine, even in patients resuming at a reduced dose.

6.3.3 Anorexia/Vomiting:

For grades 1-4 anorexia/vomiting, study drug should be continued with initiation of antiemetic therapy. If drug needs to be held until patient can tolerate drug with supportive care, patient may resume at same dose level. If antiemetics do not bring relief, then the dose should be reduced one level. Patients with grade 3 or 4 anorexia/vomiting that do not respond to supportive care should be discontinued from study drug, but will remain on study for follow-up procedures until initiation of another therapy.

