7. DRUG FORMULATION AND ADMINISTRATION

7.1 Pyrimethamine

7.1.1 Description

The chemical name of pyrimethamine is 5-(4-chlorophenyl)- 6-ethyl-2,4-pyrimidinediamine. It acts as a folate antagonist and a STAT3 inhibitor.

Pyrimethamine is well absorbed orally with peak levels occurring between 2 to 6 hours following administration. It is eliminated slowly and has a plasma half-life of approximately 96 hours. Pyrimethamine is 87% bound to human plasma proteins.

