11. ADVERSE EVENT REPORTING REQUIREMENTS

11.1 General

Adverse event collection and reporting is a routine part of every clinical trial. This study will use the descriptions and grading scales found in the CTEP Active Version of the NCI Common Terminology Criteria for Adverse Events (CTCAE) that is available at <http://ctep.cancer.gov/reporting/ctc.html> and the IWCLL criteria for hematologic malignancies as outlined in Section 6.3.1.

Information on all adverse events, whether reported by the participant, directly observed, or detected by physical examination, laboratory test or other means, will be collected, recorded, followed and reported as described in the following sections.

Adverse events experienced by participants will be collected and reported from initiation of study medication, throughout the study, and within 30 days of the last dose of study medication. Participants who experience an ongoing adverse event related to a study procedure and/or study medication beyond 30 days will continue to be contacted by a member of the study team until the event is resolved, stabilized, or determined to be irreversible by the participating investigator.

Participants should be instructed to report any serious post-study event(s) that might reasonably be related to participation in this study. The investigator should notify the IRB and any other applicable regulatory agency of any unanticipated death or adverse event occurring after a participant has discontinued or terminated study participation that may reasonably be related to the study.

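### Section 3.1.9 ends contraception with an undefined study participation and sets no interval after the last dose of an animal teratogen with a 96-hour half-life

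*Combined protocol and SAP*

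**What the plan says.** Section 3.1.9 gives the reason for contraception (human fetal effects unknown, teratogenic in animals) and sets its period: "prior to study entry and for the duration of study participation". The pregnancy-reporting request has the same limit: "Should a woman become pregnant or suspect she is pregnant while participating in this study, she should inform her treating physician immediately". Section 3.2.8 adds that the drug is class C, with teratogenic or abortifacient potential.

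Sections 2.1 and 7.1.1 both give the half-life. In the latter: "It is eliminated slowly and has a plasma half-life of approximately 96 hours".

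No section defines the end of study participation. The relevant text is:

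- Section 5.5 lists reasons for ending treatment, including "Participant decides to withdraw from the study".
- Section 5.7: "Participants will be removed from study when any of the criteria listed in Section 5.5 apply".
- Section 5.6: "Participants will be followed until initiation of their next therapy or until death, whichever occurs first". It then adds lifelong tracking of survival status.
- Section 6.3.3, on patients taken off drug for uncontrolled anorexia or vomiting, says they "will remain on study for follow-up procedures until initiation of another therapy".
- Section 11.1 collects adverse events "within 30 days of the last dose of study medication", and Section 11.5.1 applies the same window to serious events. Both sections treat participation as something a participant can discontinue.

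**The concern.** A contraception rule for a teratogenic drug should run until the drug has cleared, so its end should be counted from the last dose. This rule instead ends with an administrative status that the protocol does not define. Two things follow. Sites may tell participants different things about when contraception can stop. Also, some participants can comply fully and still conceive while exposed. A pregnancy that begins after participation ends need not be reported unless it leads to an adverse outcome that another rule captures. What is at stake is participant and fetal safety; the trial's inference is not involved.

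**Working it through.** **Step 1: when does the duty end?** The plan states no figure to reproduce, so the first check sets the sections side by side.

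| Reading of participation | Basis | Duty ends | Minimum time after last dose |
|---|---|---|---|
| Ends at removal from study | 5.7 with 5.5 | At or near the last dose | None |
| Ends at next therapy or death | 5.6; 6.3.3 for one toxicity | Start of next therapy | None |
| Lasts as long as survival tracking | 5.6 | Death | Lifelong, not a plausible contraception duty |

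On the second reading many participants stay covered beyond 28 days. Those who withdraw, or who are removed and soon start another therapy, can be out of the period within days on either of the first two readings.

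**Step 2: how much drug is left?** The input is a half-life of 96 h (Sections 2.1 and 7.1.1). With first-order elimination, the fraction remaining is 2^(−24 × days / half-life in hours), whatever the dose.

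| Days after last dose | Half-lives at 96 h | Remaining |
|---|---|---|
| 7 | 1.75 | 2^−1.75 = 29.7% |
| 14 | 3.5 | 2^−3.5 = 8.8% |
| 20 | 5 | 2^−5 = 3.1% |
| 28 | 7 | 2^−7 = 0.8% |
| 30 | 7.5 | 2^−7.5 = 0.55% |

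**Step 3: sensitivity to the half-life.** The documents give only an approximate value, so I take 72 to 120 h as an assumed range.

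- Day 7: 2^(−168/72) = 19.8% to 2^(−168/120) = 37.9%.
- Day 28: 2^(−672/72) = 0.16% to 2^(−672/120) = 2.1%.

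**Step 4: effect of the higher doses.** Table 1 in Section 5 adds 100 and 150 mg/day to the earlier maximum of 50 mg/day. If levels are proportional to dose (an assumption), stopping 150 mg/day instead of 50 mg/day adds 4 days × log2(150/50) = 6.3 days before any given level is reached. At day 7 the level after 150 mg/day would be 3 × 0.297 = 0.89 of the on-treatment level at 50 mg/day. At day 28 it would be 3 × 0.0078 = 0.023, or about 2.3% of that level.

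**Step 5: do other provisions close the gap?** The 30-day window in Sections 11.1 and 11.5.1 and the request in Section 11.1 to report serious post-study events would capture some adverse outcomes; Section 11.2.2 counts a congenital anomaly as serious. None of these requires contraception or the reporting of an uncomplicated pregnancy. The study calendar (Section 9, footnote 1) requires a pregnancy test only before therapy. The diary's special instructions in Appendix C do not mention contraception.

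**The case against.** The strongest reply is that the gap is narrow. The protocol keeps contact after treatment stops: Section 6.3 follows subjects removed for toxicity until next therapy or death, and Sections 8.1 and 8.2 schedule samples at the off-study visit and 2 to 4 weeks later, with a pharmacodynamic sample at three months. Section 12.1.2 has a follow-up form after the off-study form. Removal from study therefore need not end participation. This weakens the early-lapse reading, but these provisions either stop at the next therapy, do not hold a participant who withdraws, or do not define participation.

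The number exposed is unknown. Section 14 plans 20 additional Phase II patients and at most 12 additional Phase I patients, and Section 2.2 notes that CLL incidence rises with age and is higher in men. This stands: few women of child-bearing potential are likely. The rule also binds men, however, for whom the documents give no basis for choosing a washout length.

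The percentages describe residual drug and do not demonstrate harm, since no teratogenic threshold is given. That also stands. Seven half-lives is a reviewer's choice, and an agreement made at entry can only advise someone who later withdraws. Finally, the consent pages were removed before review and may state an interval. If so, Section 3.1.9 should still match it.

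**Conclusion.** The concern holds. As written, Section 3.1.9 lets a participant who withdraws or moves quickly to another therapy stop contraception with about 30% of the drug remaining at day 7 (20% to 38% over the assumed 72 to 120 h range) and 9% at day 14. The figures rest on first-order elimination at the stated half-life; the comparison between doses also assumes proportionality. The number of people affected is probably small and cannot be derived from the documents, and the fetal risk at these residual levels is not quantified. The maximum tolerated dose, the response rate and the error rates are untouched. This is a safety improvement worth making because it is cheap. Confidence is medium, mainly because the consent form could not be seen.

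**What to change.** In Section 3.1.9, have participants agree at entry to use contraception, and to report any pregnancy, through at least 28 days after the last dose of pyrimethamine, regardless of the off-study date. That is seven half-lives at the stated value. Thirty days would match the existing adverse event window and may be simpler to administer. The investigators may set a longer period, for example for men. Put the same line in the diary's special instructions (Appendix C) and check that the consent form agrees.

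The cost is one sentence in the protocol, one line in the patient instructions, and about one extra month of contraception for participants who would otherwise leave the period early.
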